## 15.6 Analysis of primary endpoint

The primary endpoint is defined as time to the first occurrence of microalbuminuria (UACR >30 mg/g and <300 mg/g) in 2 out of 3 sterile first morning void urine samples with a geometric mean of UACR >30% above initial geometric mean UACR OR geometric mean > 40 mg/g in three samples. The baseline urinary albumin-to-creatinine ratios are the geometric mean of three measurements obtained during the "run-in" period.

It is expected, that the number of patients who will drop out between randomization and occurrence of microalbuminuria will be low (<15%).

If those cases where drop out occurs before sampling during the study period, prior to unblinding the treatment code it will be specified in the statistical analysis plan, whether these patients have to be considered as a treatment failure in the analysis of the primary endpoint.

The predictive value of a positive and negative test, specificity and sensitivity of the test in relation to prediction of development of the primary endpoint will be evaluated. To assess whether CKD273 classifier (the marker) improved risk prediction of the primary outcome we determined the concordance statistic (c-statistic) and Integrated Discrimination Improvement (IDI). Both parameters measure the discriminative ability of a marker in a model to distinguish between people who will or will not develop the outcome (in case of predictive methods).

The primary endpoint will be analyzed in the total population with comparisons of high- vs. low-risk pattern and active vs. placebo treatment using a Cox proportional-hazards regression model with treatment as a fixed effect; the baseline urinary albumin-to-creatinine ratio will be logarithmically transformed (base 10) as a covariate, and a two-tailed Wald chi-square test with an alpha level of less than 0.05; hazard ratios and two-sided 95 % confidence intervals will be calculated. Kaplan Meier plots of the groups will be made.

Secondly, the analyses will be adjusted for age, gender, center, HbA1c and BP. Thirdly, further adjustment for any baseline demographic variables which are significantly different between the groups and related to albuminuria at baseline will be calculated. In addition adjustment will be made for significant changes in RAAS blockade or treatment with aldosterone receptor antagonist as concomitant medication during the study period.

A third analysis will plot and compare all three groups (low, high placebo and high active treatment) using a log-rank test.

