### 11.3 Main side effects of spironolactone

Gynecomastia may develop in association with the use of spironolactone. Development appears to be related to both dosage level and duration of therapy and is normally reversible when the drug is discontinued. In rare instances some breast enlargement may persist.

The following adverse events have been reported in association with spironolactone therapy:

Organ system	Side effect
General disorders and administration site conditions	malaise
Neoplasms benign, malignant and unspecified (including cysts and polyps)	benign breast neoplasm
Gastrointestinal disorders	gastrointestinal disturbances, nausea
Blood and lymphatic system disorders	leukopenia (including agranulocytosis), thrombocytopenia
Hepatobiliary disorders	hepatic function abnormal
Metabolism and nutrition disorders	electrolyte disturbances, hyperkalemia
Musculoskeletal disorders	leg cramps
Nervous system disorders	dizziness
Psychiatric disorders	changes in libido, confusion
Reproductive system and breast disorders	menstrual disorders, breast pain
Skin and subcutaneous tissue disorders	Stevens-Johnson syndrome (SJS), toxic epidermal necrolysis (TEN), drug rash with eosinophilia and systemic symptoms (DRESS), alopecia, hypertrichosis, pruritus, rash, urticaria
Renal and urinary disorders	acute renal failure

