### 12.4 Albuminuria treatment

All participants included in the trial are normoalbuminuric (UACR <30 mg/g). If a participant reaches the primary endpoint during the course of the study, the information will be flagged in the eCRF and the investigator will be notified.

Participants not in treatment with ACE or ARB at the time of screening should not start treatment before the primary endpoint is reached.

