## 15.5 Final analysis plan

Statistical analysis of the data will be performed by Steno Diabetes Center. A SAP will be written and signed before database lock and unblinding of the entire treatment code. Methods for imputation and type of censoring will be clarified in the SAP.

The primary efficacy analysis will be performed for all patients randomized, which is the intent-to-treat population. In addition, the primary and secondary efficacy endpoints will also be analyzed for the per-protocol population. The per-protocol analysis population includes all patients who were randomized into the double-blind study received study medication for at least 3 days.

For all analyses a p value <0.05 is considered significant.

Tables will be created for baseline variables, and comparisons performed between low- and high-risk population, and in the intervention group for active vs. placebo treatment. Furthermore, tables with observations from study visits will be provided for the observational part and for the intervention study.

Analyses not described here or in the SAP will be considered exploratory/post hoc analyses.

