## 15.7 Analysis of secondary endpoints

All secondary endpoints as described in section 5.5 will be analyzed to test if there is a difference in development of endpoints over time between a) active vs. placebo treated patients, and b) high-risk and low-risk population based on CKD273. As described in section 15.5.1 the analyses will initially compare low-risk with high-risk placebo treated patients, and secondly all high-risk patients. Adjustments will be performed as for the primary endpoint.

In addition to time to event (survival) analyses for discrete endpoints, analyses will evaluate the change over time in geometric mean UACR as slope analyses unadjusted as well as adjusted for confounders as described for the primary endpoint, comparing slope in the high-risk population with active vs. placebo and between low-risk and high-risk population the total population. Similar analyses will be performed with change in eGFR with time as the endpoint.

In the analyses with time to cardiovascular events, only time to first event in case of more than one event in a patient will be included.

In addition to the above described analyses comparing endpoints or slopes in high- vs. low-risk population or active vs. placebo, explorative analyses will also evaluate if the CKD 273 pattern and other baseline variables or changes in variables from baseline to 13 weeks visit in the high-risk population are predictive of development of endpoints.

Further analyses may be described in the SAP before database lock.

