#### 24.2.4 Additional treatment

Consider reduction in ACE or ARB or increase in diuretics.

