#### **24.3.2 Additional treatment**

Consider treatment with non-potassium sparing diuretics (or increased doses of ongoing treatment).

Consider treatment with natriumpolystyrenesulfonat.

Reduce treatment dose of ACE inhibitor or Angiotensin II receptor blocker (ARB)

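### Protocol 15.6 pre-specifies adjustment for on-study RAAS-blockade changes, which treatment or outcome can cause; the SAP should state that it is dropped

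*Protocol*

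**What the plan says.** Protocol 15.6 sets out a Cox model with log baseline UACR. A second adjustment adds age, gender, centre, HbA1c and blood pressure, and a third adds imbalanced baseline demographics. It then continues: "adjustment will be made for significant changes in RAAS blockade or treatment with aldosterone receptor antagonist as concomitant medication during the study period". It does not define a significant change, or say whether the covariate is a fixed flag or time-updated.

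Protocol 15.7 extends this to the secondary endpoints: "Adjustments will be performed as for the primary endpoint". For albuminuria over time it plans "slope analyses unadjusted as well as adjusted for confounders as described for the primary endpoint".

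Other sections show what can change RAAS treatment during the study:

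- Protocol 11.3 lists "electrolyte disturbances, hyperkalemia" among the side effects of spironolactone.
- Appendix 1 says at the lower potassium band: "Consider reduction in ACE or ARB or increase in diuretics". At the next band (24.3.2) it directs that the ACE inhibitor or ARB dose be reduced.
- Protocol 12.4 has the investigator notified when a participant reaches the primary endpoint, and says: "Participants not in treatment with ACE or ARB at the time of screening should not start treatment before the primary endpoint is reached".
- Aldosterone antagonists are prohibited (12.2), and their use requires study drug to be stopped (14.6).

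The adjusted models in SAP 6.3.1, 6.3.2 and 6.4 use baseline covariates only. The SAP does not mention the RAAS-change adjustment. On status, Protocol 15.5 says: "Analyses not described here or in the SAP will be considered exploratory/post hoc analyses".

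**The concern.** A covariate that treatment or outcome can change is not a confounder. Adjusting for it blocks part of the effect of interest. It can also create an association through unmeasured factors that drive both the covariate and the outcome.

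There are two main routes:

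- **Treatment.** Spironolactone raises potassium and the ACE inhibitor or ARB is cut. This route exists however change is coded.
- **Outcome.** Microalbuminuria is reached and an ACE inhibitor or ARB is then started. For the primary endpoint this matters only with an ever/never flag, because in time-updated coding such starts fall after the event. For endpoints that follow microalbuminuria, such as macroalbuminuria, it matters under time-updated coding too, because the start marks an intermediate step.

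The aldosterone-antagonist half of the sentence adjusts for a post-randomisation deviation that itself ends study treatment.

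The low-risk group is not randomised, so in the high- versus low-risk comparison the variable is post-baseline rather than post-randomisation. The objection still applies: the aim there is the predictive value of a baseline test, and later treatment is not part of that test.

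At stake is interpretation. If RAAS changes differ by arm or risk stratum, a gap between adjusted and unadjusted hazard ratios cannot be told apart from bias due to the adjustment.

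**Working it through.** **Plan figures.** Protocol 15.1 and SAP 3.4 give 24% versus 40% events, two-sided alpha 0.05, power 0.80 and 129 per arm. With unpooled variance, (1.960 + 0.842)² × (0.40×0.60 + 0.24×0.76) / 0.16² = 129.5, which agrees. The covariate plays no part in this, so removing it changes no design number.

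**Implied hazard ratios (constant hazards).**

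- Active versus placebo: ln(0.76)/ln(0.60) = 0.537.
- High versus low risk: ln(0.68)/ln(0.915) = 4.34, where 32% is the mean of 24% and 40%, and 8.5% is the low-risk rate.

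**Assumptions.** The documents give no rates of RAAS change, so every rate below is assumed. Values are large-sample Cox limits, with follow-up scaled to one study period. The ACE/ARB cuts and macroalbuminuria come from a deterministic multistate model. The endpoint-driven starts come from 1.5 million simulated patients, with 5% of RAS-naive patients starting before the event.

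**Treatment route, primary endpoint, time-updated coding.** The shared factor is an unmeasured prognostic factor that raises both cuts and events.

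| ACE/ARB cuts, active / placebo | Event hazard after cut | Shared factor | HR unadjusted → adjusted |
|---|---|---|---|
| 5% / 5% | ×1 to ×2 | largest change found | 0.571 → 0.569 |
| 5% / 2% | ×1 | no | 0.537 → 0.537 |
| 5% / 2% | ×2 | yes | 0.577 → 0.565 |
| 15% / 5% | ×1.5 | no | 0.550 → 0.537 |
| 15% / 5% | ×1.5 | yes | 0.585 → 0.555 |
| 15% / 5%, no treatment effect | ×1 | yes | 1.000 → 0.980 |

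The fourth row shows the blocked pathway. The total effect is 0.550 because more cuts on spironolactone cost some benefit, and adjustment hides that cost. The last row is pure bias: neither treatment nor the cut has any effect, yet the hazard ratio moves below 1.

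**Outcome route.** Ranges run from 20% RAS-naive with 25% of them starting after the event, to 60% naive with 75% starting.

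| Endpoint and coding | Active vs placebo, low end | Active vs placebo, high end | High vs low risk, low end | High vs low risk, high end |
|---|---|---|---|---|
| Primary, ever/never | 0.538 → 0.542 | 0.536 → 0.621 | 4.368 → 4.313 | 4.331 → 3.359 |
| Primary, time-updated | no change | no change | no change | no change |
| Macroalbuminuria, time-updated | 0.572 → 0.578 | 0.572 → 0.676 | 4.009 → 3.935 | 4.009 → 2.920 |

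The macroalbuminuria row assumes that it occurs only after microalbuminuria, at hazard 0.3 per study period (5.9% placebo, 3.4% active), and that the start itself has no effect. The middle case (40% naive, 50% starting) gives 0.572 → 0.608. With no treatment effect, the outcome route produces essentially no shift (ever/never: 1.002 → 1.003 and 0.999 → 1.001; macroalbuminuria: 1.000 → 1.000).

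**Separate check.** Simulated trials of 300 patients, under different and stronger assumptions and with fixed flags, also gave shifts in both directions:

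- Post-endpoint starts in 60% of all patients with an event: 0.537 → 0.645, with power falling from 0.85 to 0.54.
- Early cuts in about 20% versus 6%, with hazard ×1.5 and a shared factor: 0.589 → 0.523.
- More RAS intensification for blood pressure on placebo (about 28% versus 16%), a further possible route given the small antihypertensive effect noted in Protocol 14.2: 0.553 → 0.577.

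**Scale.** With 150 per arm, 24% and 40% give 36 and 60 events, so SE(log HR) = √(1/36 + 1/60) = 0.21. The shift from 0.585 to 0.555 is ln(0.585/0.555)/0.21 = 0.25 SE. The shift from 0.536 to 0.621 is 0.70 SE. For macroalbuminuria, about 9 and 5 events give SE = √(1/9 + 1/5) = 0.56, so 0.572 to 0.676 is 0.30 SE.

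**The case against.** The strongest reply is that the SAP has already dealt with this. Each SAP adjusted model lists baseline covariates, and SAP 6.3.2.1 restricts the primary intervention model to baseline eGFR and UACR. On this view only a protocol sentence that nobody will run remains, and reading 15.5 as preserving it is an inference. The effect is also small beside the standard error. Protocol 12.3 asks for ACE/ARB to stay unchanged if possible. Appendix 1 says only to consider a reduction at the lower band. Protocol 12.4 permits a start after the endpoint but does not order one. Finally, whether uneven co-medication explains a difference is a fair supplementary question, which better specification would keep alive.

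Much of this stands as a limit on reach. The primary result is not threatened, plausible shifts are mostly small, and the outcome route depends on coding and prescribing habits. The fixed-flag result of 0.645 did not restrict starts to RAS-naive patients, to whom 12.4 applies, so it should carry little weight. The extension to slopes depends on counting an on-study change among the confounders that 15.7 mentions, and no slope shift was computed.

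The core is not answered. Protocol 15.6 says the adjustment will be made, and SAP silence does not withdraw it. Time-updated coding leaves the hyperkalaemia route open, and for macroalbuminuria the outcome route too. The protocol does not frame the analysis as a mediation or intercurrent-event question with its own estimand.

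**Conclusion.** The concern holds. As written, Protocol 15.6 yields a supplementary hazard ratio that is neither the total treatment effect nor the predictive value of the baseline test, and 15.7 passes the same adjustment to the secondary endpoints. The damage is confined to those analyses.

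The true size is unknown, because it depends on rates the documents do not give. At modest assumed rates the shift is 0 to 0.012. It reaches about 0.03 with ACE/ARB cuts in 15% versus 5%, a raised hazard after the cut and a shared prognostic factor. It approaches 0.1 only with high start rates, combined with an ever/never flag for the primary endpoint, or for macroalbuminuria. The case rests on the logic of the adjustment rather than on a large number. It should be corrected because an analysis that counts as pre-specified could be reported as planned and could not be interpreted.

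**What to change.** 1. **Protocol 15.6.** Delete the sentence containing "adjustment will be made for significant changes in RAAS blockade or treatment with aldosterone receptor antagonist as concomitant medication during the study period". Replace it with: *Adjustment covariates are limited to values measured at or before baseline.* Section 15.7 then inherits baseline adjustment only.
2. **SAP 6.3.** Add: *The adjustment in protocol 15.6 for RAAS-blockade changes or aldosterone receptor antagonist use after baseline is not carried forward. These changes are tabulated by treatment arm and by risk stratum, for description only.*

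If the protocol can no longer be amended, the SAP addition is enough. If the effect of co-medication is itself of interest, it needs a pre-specified intercurrent-event analysis with its own estimand, not a covariate.

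The cost is one protocol sentence replaced, two SAP sentences added, and one descriptive table from concomitant-medication data already collected at each visit. No SAP model, sample size or alpha changes.

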## 15.7 Analysis of secondary endpoints

All secondary endpoints as described in section 5.5 will be analyzed to test if there is a difference in development of endpoints over time between a) active vs. placebo treated patients, and b) high-risk and low-risk population based on CKD273. As described in section 15.5.1 the analyses will initially compare low-risk with high-risk placebo treated patients, and secondly all high-risk patients. Adjustments will be performed as for the primary endpoint.

In addition to time to event (survival) analyses for discrete endpoints, analyses will evaluate the change over time in geometric mean UACR as slope analyses unadjusted as well as adjusted for confounders as described for the primary endpoint, comparing slope in the high-risk population with active vs. placebo and between low-risk and high-risk population the total population. Similar analyses will be performed with change in eGFR with time as the endpoint.

In the analyses with time to cardiovascular events, only time to first event in case of more than one event in a patient will be included.

In addition to the above described analyses comparing endpoints or slopes in high- vs. low-risk population or active vs. placebo, explorative analyses will also evaluate if the CKD 273 pattern and other baseline variables or changes in variables from baseline to 13 weeks visit in the high-risk population are predictive of development of endpoints.

Further analyses may be described in the SAP before database lock.

## 15.8 Analysis of safety endpoints

The exposure of study treatment will be characterized by number of administrations and the cumulative dose for both treatment groups.

AEs will be coded using the MedDRA via MARVIN.

An overview of all eCRF-documented AEs will be prepared. For all these categories of AEs (see section 13.3) separate frequency tables will be provided presenting the AEs by MedDRA preferred terms, SOC and treatment groups.

In addition AEs leading to death and AEs leading to discontinuation of study medication will be summarized for the two treatment groups.

Safety laboratory results will be classified by grade according to CTCAE version 4.0. The worst on-study grades after the first dose of study medication will be summarized. Only patients with post-baseline laboratory values will be included in these analyses. Furthermore, summary statis-

tics (mean, median, SD, SEM, range) will be calculated for the laboratory values at the various visits and for the changes from baseline. Baseline values are defined as the last available value prior to start of study treatment.

Corresponding descriptive summaries will be generated for vital signs.

## **16 QUALITY ASSURANCE**

### **16.1 Site monitoring**

To ensure compliance with the protocol, to legal and regulatory requirements applicable for clinical trials and with the ethical principles of Declaration of Helsinki and ICH-GCP, monitoring visits for source data verification by members of HCTC will be scheduled to take place during the study.

Before the start of the study, pre-study visits will be conducted and each participating center will be trained via initiation visits. Further visits during the study will be performed, according to patient recruitment rate. Finally, after the last patient has completed the study a close-out visit will be conducted.

During site visits, the monitor should review drug accountability records and document retention (investigator's study file) as well. Additionally, the monitor should observe clinical study procedures and discuss any problems with the investigator(s) and/or the trial staff.

All original data should be readily available for review during scheduled monitoring visits. Reviewing the eCRFs for completeness and clarity, and cross-checking with source documents will be required, and the investigator assures HCTC of support at all times.

### **16.2 Site audit an inspections**

Audits (by the sponsor) and inspections (by regulatory authorities) may be performed in order to verify that the clinical study is performed according to the study protocol as well as to other applicable regulatory requirements. The auditor or inspector is independent in regard to personnel involved in the conduct of this clinical trial. This may occur at any time from start to after closure of the study.

## **17 ETHICAL, REGULATORY AND ADMINISTRATIVE ASPECTS**

### **17.1 Investigator responsibilities**

Investigator responsibilities are set out in ICH-GCP and in the Consortium Agreement (project no. 279277).

Investigators must enter study data in eCRFs within 2 weeks after the visit. The investigator will permit study-related monitoring visits and audits by the sponsor or its representatives as well as regulatory inspection(s). The investigator must provide direct access to the study center's facilities, to source documents, and to all other study documents.

The investigator or a designated member of the investigators staff must be available at some time during monitoring visits to review data and resolve any queries and to allow direct access to the patient's records (e.g., medical records, office charts, hospital charts, and study related charts) for source data verification. The data collection must be completed prior to each monitoring visit so that the accuracy and completeness may be checked.

The investigators reporting responsibilities regarding AEs are described in section 13.

### **17.2 Regulatory requirements**

The study will be performed under ICH-GCP requirements and national laws and regulations depending on each country.

### **17.3 Justification for selection criteria**

The justification of the second inclusion criteria limiting the age of eligible patients to 75 years is due to the expected prevention potential of the trial. Patient included in the trial must have persistent normoalbuminuria and therefore no sign of diabetic nephropathy at the time of inclusion. The time course of diabetic nephropathy will usually be >10 years from the onset of microalbuminuria to overt kidney disease. Since the aim of the study is to prevent kidney disease (onset of microalbuminuria) we consider it unethical to start preventive medical treatment in patient where the potential onset of disease is after the expected life time.

